Appendix 7 – Proposed Data Sheet

- 1. Participant Trial Number
- 2. Patient/Tumour Baseline Characteristics:
 - Age
 - Gender
 - Performance Status (ECOG)
 - Co-morbidities
 - Substance use
 - Body Mass Index
 - Histological type of malignancy (SCC, Adenocarcinoma, Other)
 - Reason for inoperability (metastases, locally advanced, poor performance status, or other)
 - Position of malignancy (endoscopic measurement in centimetres from the incisors)
 - Length of tumour

3. Pre-stenting Scores:

- Dysphagia (pre-stenting)
- GerdQ (pre-stenting)
- Pain (pre-stenting)
- Coughing (pre-stenting)
- 4. Stent Insertion:
 - Stent characteristics: anti-reflux vs conventional, length, diameter and brand name of stent

- Immediate technical success rate
- Immediate stent insertion complications:
 - Bleeding
 - Perforation
 - Incorrect stent placement
 - Other
- 5. Day 1 Post-Stenting:
 - Scintigraphy Results
 - Oesophageal Clearance
 - Oesophageal Reflux
 - Secondary Clearance
 - Gastric Emptying
 - Dysphagia score (day 1)
 - Pain score (day 1)
 - Coughing score (day 1)

6. Week 1 Post-stenting:

٠

- GerdQ Score (week 1)
- Dysphagia Score (week 1)
- Pain Score (week 1)
- Coughing Score (week 1)

7. Week 2 Post-stenting:

- GerdQ Score (week 2)
- Dysphagia Score (week 2)
- Pain Score (week 2)
- Coughing Score (week 2)

8. Week 4 Post-stenting:

- GerdQ Score (week 4)
- Dysphagia Score (week 4)
- Pain Score (week 4)
- Coughing Score (week 4)
- 9. Week 8 Post-stenting:
 - GerdQ Score (week 8)
 - Dysphagia Score (week 8)
 - Pain Score (week 8)
 - Coughing Score (week 8)

10. Outcomes:

- Stent-related complications during the follow-up period:
 - Bleeding
 - Perforation
 - Migration
 - Stent Occlusion and Cause Thereof
 - Perforation
 - Other
- Survival outcome at 8 weeks (alive or dead)

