What is less controversial, are the data on safety and efficacy at dysphagia improvement using antireflux stents. The pooled data of the meta-analysis show that there are no significant differences in stent-related complications between the anti-reflux stents and conventional stents, specifically stent migration, bleeding and stent occlusion ¹. Improvement in dysphagia was similar between the two stents, actually slightly favouring the anti-reflux stent group, but not reaching statistical significance. Another systematic review and meta-analysis focusing specifically on oesophageal stents placed for malignant obstruction, showed that treatment-related deaths were actually reduced when anti-reflux stents were used ²⁰. Thus, using anti-reflux oesophageal stents does not raise any additional safety concerns when compared to conventional stents. While research in high income countries is focused on the management of early oesophageal malignancies, this is not appropriate in the South African setting where the vast majority of patients are irresectable at initial presentation. Local research is significantly limited²¹ and there is a paucity of data from South Africa, and Africa as a whole, as regards the palliative management of malignant oesophageal dysphagia. Specific evidence on the use of anti-reflux stents is absent. Further research is thus invaluable in assessing if the palliative care of these patients can be improved by using anti-reflux stents.

This prospective randomised controlled trial aims to compare the incidence of symptomatic volume GOR after the use of anti-reflux oesophageal covered metal stents versus conventional oesophageal covered metal stents for lower oesophageal malignant strictures in a South African tertiary referral centre with a high rate of palliative stenting for advanced oesophageal carcinoma.

AIM AND OBJECTIVES

Aim

This prospective randomised controlled trial will aim to compare symptomatic volume GOR, when using anti-reflux oesophageal stents versus conventional oesophageal stents, in the palliative management of patients with lower oesophageal or OGJ carcinomas.

Primary Objective/Hypothesis to be Tested

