Randomisation will be done using opaque, sealed envelopes with computer-generated random numbers in blocks of 20 (10:10). Patients will be randomised to either receive a conventional oesophageal stent or an anti-reflux oesophageal stent. Other than the anti-reflux mechanism, all other parameters of the two stents will be the same – both stents will be fully covered Nitinol self-expanding metal stents designed for deployment in the oesophagus (conventional stent: Taewoong Niti-S Esophageal Covered Stent, distributor: First Medical Company [Global Medical Device Nomenclature Code 61751] and anti-reflux stent: Taewoong Niti-S Esophageal Covered AR Stent, distributor: First Medical Company [Global Medical Device Nomenclature Code 61751] and anti-reflux stent: Taewoong Niti-S Esophageal Covered AR Stent, distributor: First Medical Company [Global Medical Device Nomenclature Code 48136]). Both stent types come in a standard length of 120mm. Both of these stents are available and currently form part of the standard of care at GSH, although the stent selection is determined by stent availability and endoscopist preference – the conventional stent is generally favoured. Both are approved by SAHPRA as part of First Medical's list of approved devices they can import into and distributed in South Africa.

The technique of stent deployment will also be the same for both anti-reflux and conventional stents. Stent position and deployment success will be confirmed after stent placement, using water-soluble contrast injected through the stent under fluoroscopy – this will confirm the distal stent position crossing the OGJ. The patient will remain unaware of which type of stent they are receiving. The progress of the trial will be documented according to the CONSORT 2010 flow diagram²².

Follow-up

Technical success of the stent insertion will be confirmed using fluoroscopy immediately after insertion. Any insertion-related complications will be documented. All patients will be appropriately observed in the gastrointestinal unit after the procedure and then admitted to the ward for overnight observation. They will undergo scintigraphy the following day (day 1 post the procedure) and then if deemed well enough will be either discharged home or referred back to their referring hospital. The follow-up period will subsequently continue for a total of 8 weeks.

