Patients with palliative oesophageal cancer are in most instances frail and have a significantly limited life expectancy. It is thus imperative upon discharge, that further research-related follow-up should not inconvenience the patient nor have a negative effect on their quality of life. Furthermore, many of the patients treated at GSH have limited financial means to afford repeated follow-ups at the hospital. For these reasons, subsequent follow-up after discharge, will be done telephonically. Patients will be phoned at 1, 2, 4 and 8 weeks post stent insertion and will be asked about any symptoms related to the stent insertion, and have an assessment of symptomatic GOR using the GerdQ questionnaire ⁸, dysphagia, cough and pain levels at each telephonic follow-up. Telephonic follow-up of these patients will be done by the Clinical Coordinator, who is blinded to which type of stent the patient has received.

All patients will also be referred to the GSH Palliative Care Team. With any symptom reported by a patient or family member that is deemed to possibly require further intervention or treatment, the patient will be requested to return for an evaluation or appropriately managed according to the Palliative Care Distress Algorithm (Appendix 1). All complications will be managed as per standard treatment routinely employed for such a complication at GSH. Any such complications will be documented.

OUTCOME MEASURES

Primary Outcome Measure

The primary outcome will be patient-reported rates of symptomatic volume GOR and objectively measured volume GOR in both study groups. Patient-reported symptomatic volume GOR will be assessed using the validated GerdQ questionnaire (Appendix 2)⁸. This questionnaire has been chosen has it is simple, easy to understand and includes only 6 questions, which are all reflux-related. This questionnaire will be administered to the patient prior to the procedure, to establish a baseline. It will then subsequently be telephonically administered at the scheduled telephonic follow-ups at weeks 1, 2, 4 and 8. The GerdQ questionnaire enables the patient to provide a score at each follow-up interaction which can then be documented and the mean scores between the two groups can then be compared.

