GOR will also be objectively measured on day 1 post stent insertion using scintigraphy. The proposed protocol for scintigraphy is described in Appendix 3. This modality has been chosen as its accuracy compares favourably to pH monitoring⁹, but is much less invasive. It requires the patient to swallow a meal of soft, runny porridge and then undergo imaging. pH monitoring is invasive, requiring the insertion of an uncomfortable nasal probe which stays in-situ for 24 hours, increasing discomfort for the patient but also increasing the hospital stay by a further 24 hours. It is thus deemed inappropriate in this setting.

Secondary Outcome Measures

The secondary outcomes that will be assessed will include immediate technical success rate and any complications related to the stent insertion, subsequent stent-related complications, patient-reported dysphagia score prior to stent insertion, on day 1 post-insertion and then at each of the scheduled telephonic follow-ups and lastly, patient survival at 2 months post stent insertion. Dysphagia assessment will be done using the modified dysphagia scale first published by Mellow and Pinkas and validated for assessing dysphagia after metal stent insertion for oesophageal cancer (Appendix 4)²³. Furthermore, an assessment of the patient's pain level and whether they are coughing will also be documented, using validated pain²⁴ and cough scores²⁵ and pain (Appendix 5 & 6).

Data Collection

The following data parameters will be collected:

- Age
- Gender
- Performance status25 and BMI of the patient at time of stent placement
- Histological type of malignancy (e.g. adenocarcinoma, squamous cell carcinoma or other)
- Reason for inoperability: metastases, locally advanced or poor performance status
- Position of oesophageal malignant stricture (endoscopic measurement in centimetres from the incisors)
- Patient-reported degree of dysphagia prior to stenting
- Patient-reported GerdQ score pre-stenting
- Stent characteristics: anti-reflux vs conventional, length, diameter and brand name of stent
- Immediate technical success rate
- Immediate stent insertion complications:
 - o Bleeding
 - Perforation
 - o Other

- Subsequent stent-related complications during the follow-up period:
 - o Bleeding
 - Perforation
 - Migration
 - Stent occlusion and cause thereof
 - \circ Other
- Quantitative assessment of volume reflux as per scintigraphy (on day 1)
- GerdQ score at follow-up at week 1, 2, 4 and 8

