- Dysphagia score on day 1 post stent-insertion and at follow-up weeks 1, 2, 4 and 8
- Patient survival outcome at 8 weeks
- Cough and pain score pre-insertion, on day 1 and at 1, 2, 4 and 8 weeks

Data Safety and Monitoring

A password-protected computer-based registry will be created using REDCap (Research Electronic Data Capture). No paper-based data collection sheets will be used to record the data and analysis will take place directly from the registry after data exportation into an appropriate statistical software programme such as SPSS or Stata.

To protect patient confidentiality:

- Access to the registry will be password protected and will only be accessed by investigators on this study.
- Data extracted from the registry to SPSS / Stata will be anonymised and patient details will only be identifiable from their designated trial number.

Research Procedures and Data Collection Methods

All data will be prospectively entered into the electronic registry at the time of stent insertion and at the defined post-insertion follow-up periods. Patients will be contacted telephonically at the defined post-insertion follow-up periods by the Clinical Coordinator. Other than the scintigraphy, this study will require no biological specimens or further special investigations specifically for the purposes of the research project.

ETHICAL CONSIDERATIONS

There will be no additional risk, cost or investigations to the patients if they agree to be included in the trial. Patients will only be included in the study after being informed about the study and completing the consent form. Patient confidentiality will be maintained. The study will be conducted in accordance with:

- Guidelines for Good Clinical Practice (GCP) in the conduct of Clinical Trials in Human Participants in South Africa. Latest Edition, 2020 (released June 2021).
- The Department of Health: Ethics in Health Research: Principles Structures and Processes 2004
- The Helsinki Declaration.

All efforts will be made to publish the results in an international or local academic peer-reviewed journal and submitted for presentation at an appropriate national or international congress. Although the patients who are included in the study may not benefit directly from their participation, the results may help us manage future patients more effectively.

Description of risks and benefits

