This trial will not involve a pharmaceutical product or device that requires repeated administration. Both stents are inserted as a once-off procedure and unless there is an unforeseen complication (such as stent migration or patient intolerance of the stent necessitating removal), these stents usually stay in-situ indefinitely. With the unfortunately short life expectancy for this group of patients, most participants will require a single stent insertion and will then die with the stent still in-situ. This means that once the trial period is over, they will still continue to have the benefit of the stent regardless of when the trial ends. If the anti-reflux stents are proven to significantly reduce GOR, those participants in the conventional stent group will however not be offered an anti-reflux stent if the stent they have received is still functional and without problems. This is because the procedure of exchanging one stent for another carries significant risks and in this vulnerable group of patients such a stent exchange procedure would not be justified.

Statistical Analysis

Data will be captured using the REDCap electronic data capturing software licensed to the University of Cape Town. All data exploration and analysis will be done using an appropriate statistical software programme such as SPSS (version 27.0, IBM, USA). Statistical significance will be set as p <0.05. Recorded data will be expressed as mean (SD), or median (interquartile range) when non-normally distributed (continuous data). Where continuous data are non-normally distributed, variables will be logarithmically transformed prior to inclusion in multivariable statistical analysis. Dichotomous variables will be expressed as proportions or percentages. Baseline demographic and clinical characteristics between the anti-reflux stent and the conventional stent group will be compared using appropriate statistical tests based on the nature of the data as well as distribution thereof. GOR scores between the two groups will be assessed using inferential statistics with the hypothesis that the anti-reflux stent group will have reduced reflux compared to the conventional stent group. In addition, survival analysis will be performed with visual representation using Kaplan Meier curves.

Sample Size

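### No procedure or data field covers a fatal complication after discharge, so such events may be missed and cannot be identified as fatal or stent-related

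*Combined protocol and SAP*

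**What the plan says.** The Secondary Objectives and Secondary Outcome Measures sections compare stent-related complications, later complications and survival between the arms.

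Under Follow-up, patients stay overnight, have scintigraphy on day 1, and are then "either discharged home or referred back to their referring hospital". Scheduled contact after that is by telephone: "Patients will be phoned at 1, 2, 4 and 8 weeks post stent insertion and will be asked about any symptoms related to the stent". GerdQ, dysphagia, cough and pain are also scored at each call.

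The same section gives other routes. Insertion complications are documented, symptoms raised by a patient or family member can lead to recall or management, and complications managed at the hospital are documented.

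Death appears in three places:
- Secondary Outcome Measures: "patient survival at 2 months post stent insertion".
- Data Collection: "Patient survival outcome at 8 weeks".
- Appendix 7, item 10: "Survival outcome at 8 weeks (alive or dead".

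Neither data list includes date of death, cause of death, stent-relatedness, or a fatal/non-fatal outcome for a complication. The Statistical Analysis section nevertheless says that "survival analysis will be performed with visual representation using Kaplan Meier curves".

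**The concern.** The person scheduled to report a complication is the patient. Someone who bleeds, perforates or obstructs at home or at the referring hospital, and dies before the next call, cannot report it. Unless a relative or hospital volunteers the event, the record shows a death and no complication. If the event is captured, the record shows a complication and a death, with nothing to link them. The severest events are the most exposed to this.

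The call wording is a smaller weakness. Patients "will be asked about any symptoms related to the stent insertion", which leaves attribution to them. A bleed blamed on the tumour, or a chest infection, might not be offered.

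At stake is the completeness of the secondary safety comparison, and any description of stent-related deaths by arm. The introduction itself treats such deaths as relevant when it reports from a meta-analysis that "treatment-related deaths were actually reduced when anti-reflux stents were used". Information not gathered at the time cannot be recovered at analysis.

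**Working it through.** **Denominator.** The Sample Size section gives a difference of 2 GerdQ points, SD 3, alpha 5% and power 80%. With a two-sided normal approximation, n per arm = 2 × (1.960 + 0.842)² × 3² / 2² = 35.3, rounded up to 36, so 72 in total. The plan's figure is reproduced. It serves here only as the number at risk.

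**Expected deaths by week 8.** The introduction gives median survival of 15 weeks from diagnosis and 10.7 weeks with complete obstruction. Assume exponential survival from stenting with these medians: S(t) = 0.5^(t / median), and deaths = 72 × (1 − S(8)).

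| | Median 15 weeks | Median 10.7 weeks |
|---|---|---|
| S(4) | 0.831 | 0.772 |
| S(8) | 0.691 | 0.596 |
| Dead by week 8 | 30.9% | 40.4% |
| Deaths of 72 | 22.3 | 29.1 |
| Deaths per 36, if equal by arm | 11.1 | 14.6 |
| Deaths in weeks 0–1, 1–2, 2–4 | 3.3, 3.1, 5.8 | 4.5, 4.2, 7.7 |
| Deaths in weeks 4–8: 72 × (S(4) − S(8)) | 10.1 | 12.7 |

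The longest gap between calls, weeks 4 to 8, holds about 10 to 13 of the deaths.

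**Fatal stent events.** The documents give no share of deaths involving a stent event. If that share is 5% to 20% (assumption), the total over both arms runs from 0.05 × 22.3 = 1.1 to 0.20 × 29.1 = 5.8. The number missed is this total times the fraction that the family and hospital routes fail to catch. That fraction is unknown and can be anything from 0 to 1, so the missed count is 0 to about 6.

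**What full capture could show.** Take the top of the range, six events, split 5 to 1. The two-sided Fisher p-value is 2 × [C(36,6) + 36 × C(36,5)] / C(72,6) = 2 × (1,947,792 + 13,571,712) / 156,238,908 = 0.20. Even complete data would support description only.

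**Kaplan-Meier.** The curves need a time of death for each patient who dies. A status at 8 weeks does not supply it.

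**The case against.** The strongest reply is that the telephone is not the only source. Insertion complications are documented, an overnight stay follows, family members can raise symptoms, and complications managed at the hospital are documented. The complications list in Appendix 7 has an entry for other events and is not limited to survivors. All of this stands. A reader might infer that fatal complications drop out of the safety comparison altogether; the documents do not support that. But the family route depends on someone volunteering a symptom and serves management. It is not a procedure for finding out what happened after a death.

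Second, the calls ask about dysphagia, cough and pain whatever the patient believes the cause to be, so occlusion, aspiration or perforation may show there. This stands and weakens the attribution point. Bleeding is the event without an obvious prompt.

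Third, the caller is blinded and both arms follow the same schedule. A reader might infer a bias between arms; nothing in the documents shows one. All deaths known at 8 weeks still enter the survival comparison.

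Fourth, treatment-related death is background in the introduction, not a listed outcome. A reader might infer that better collection would let this trial confirm or refute the cited difference. With at most about six events in 72 patients on the assumed range, it would not.

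Fifth, some absence cannot be verified. The content of Appendix 1 and the consent form are not in the text available, so a relative's number may already be collected. Appendix 7 is labelled as proposed. That makes it easy to amend, but the Data Collection list in the main text has the same gap.

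**Conclusion.** The point holds as possible under-ascertainment of a secondary outcome. After discharge, scheduled ascertainment rests on the patient answering a call. No stated procedure applies once the patient has died or cannot be reached, and the listed fields cannot mark a complication as fatal or a death as stent-related. With about 22 to 29 deaths expected among 72 patients by week 8, fatal complications outside the hospital may be missed.

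The death count rests on exponential survival and on medians from cited cohorts, one measured from diagnosis. A reader might infer that the true count is higher because stenting comes after diagnosis. Patients too unwell for intervention or sedation are excluded, though, so the direction is not known. The 0 to about 6 missed events rests on an assumed 5% to 20% share and an unknown capture rate. It should not be read as a predicted loss.

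The primary GerdQ comparison and the sample size are not affected. This is a worthwhile, low-cost improvement in data collection.

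**What to change.** 1. Record a relative's telephone number at consent, where the plan already expects family to be present.
2. After a death or an unanswered call, have the blinded coordinator ask the relative or the referring hospital a fixed list: bleeding, perforation, migration, occlusion, chest infection or aspiration, admission, re-intervention.
3. Ask the patient the same list at each scheduled call, whatever the believed cause.
4. Add to the Data Collection list and Appendix 7: date of death (also needed for the Kaplan-Meier curves), cause of death, and death possibly stent-related (yes, no or unknown).
5. Report stent-related deaths by arm descriptively.

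The cost is protocol, consent and REDCap wording, slightly longer scheduled calls, about 22 to 29 enquiries after deaths on the assumptions above, and an unknown number for living patients who cannot be reached. The existing coordinator can make them. Consent wording may need to cover contact with relatives and referring hospitals. Cause of death from a relative will sometimes be uncertain, which is why an unknown category is needed.
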